12. Study Organisation/ Trial Monitoring and Management Strategy	27
12.1 Responsibilities	27
12.2 Start date	28
12.3 Patient screening and enrolment	28
12.4 Patient withdrawal.....	29
12.5 Study duration	29
12.6 End of study	30

13. Safety reporting	30
14. Evaluation of Outcome/Statistical Considerations	30
14.1 Sample size.....	30
14.2 Analysis plan	31
14.3 Study monitoring	32
15. Regulatory & Ethics Committee Approval	33
15.1 Ethical considerations.....	33
15.2 Informed consent.....	34
15.3 Patient confidentiality.....	34
16. Data Handling and Record Keeping	35
16.1 Investigator Signatory Obligations.....	35
16.2 Data Handling.....	35
16.3 Study Documentation and Archive	36
16.4 Quality assurance/audit.....	36
16.5 Annual reporting to REC	37
16.6 Sample labelling, storage and destruction	37
16.7 Use of information	37
17. Financing, Indemnity & Insurance	37
18. Publication Policy	38
19. Abbreviations	38
20. Protocol Summary of Changes.....	40
21. References	41

1. Protocol synopsis

Study title: Cancer: Rapid Diagnostics and Immune assessment for SARS-CoV-2

Chief investigator: [name]

Study centres: The Royal Marsden NHS Foundation Trust

Study period: Approximately 1 year

Follow up duration: Up to 84 days

Main objective: This observational study will investigate how host cancer status and immune phenotype links to SARS-CoV-2 infection clinical presentation, seroconversion, and viral clearance. The study will also evaluate rapid antigen/antibody lateral flow tests.

Methodology: Arm A: Suspected acute COVID-19 infection

Throat/nose swabs, saliva and blood will be collected from patients undergoing investigation for suspected SARS-CoV-2 infection at the Royal Marsden NHS Foundation Trust on Day 0. Patients who are positive for SARS-CoV-2 by throat/nose RT-PCR or have a high clinical suspicion for acute COVID-19 will have further samples collected on D7 (if an inpatient), D14, D28, D42 and D56.

Arm B: Asymptomatic patients with no clinical suspicion of COVID-19

Blood will be collected from patients who do not have symptoms of COVID-19. Repeat blood will be collected on D28, D56 and D84.

Research tests including serology and antigen/antibody lateral flow tests will be performed at St George's University NHS Trust. Exploratory analyses including, but not limited to HLA-KIR profiling, blood immune cell activation and transcriptome and lateral flow testing will be carried out. Viral and immunological data will be collated in a link-anonymised manner and correlated to clinical outcome data. Samples will also be used to develop more rapid SARS-CoV-2 testing and assist in the future planning of ongoing or delayed treatment in cancer patients.

Number of patients:

Arm A: Up to 60 patients with confirmed diagnosis of SARS-CoV-2 by RT-PCR over the study period.

Arm B: Up to 150 patients with no clinical suspicion of COVID-19

Main inclusion criteria:

1) Suspected COVID-19 infection undergoing diagnostic testing by SARS-CoV-2 RT-PCR or within 14 days of confirmed COVID-19 infection by SARS-CoV-2 RT-PCR (Arm A) OR

No symptoms of SARS-CoV-2 infection (Arm B)

2) Metastatic or advanced solid organ malignancy, including lymphoma

OR

Early stage solid organ malignancy having received or planning to commence radiotherapy, chemotherapy or targeted agents

3) Patient is \geq 18 years of age.

4) Patient can understand the patient information sheet and is able to provide written informed consent.

Exclusion criteria

There are no exclusion criteria for this study.

Primary endpoint:

Proportion of patients, at each sample timepoint, with a positive detection of IgM and IgG specific antibodies to SARS-CoV-2. (Arms A and B)

Secondary endpoints:

To describe the clinical course of SARS-CoV-2 infection in cancer patients. This will include duration and severity of clinical symptoms, supportive treatments given, cancer treatments received and outcome of SARS-CoV-2 infection. (Arm A)

Proportion of patients, at each sample timepoint, with SARS-CoV-2 viral clearance by throat/nose swab by RT-PCR. (Arm A)

Time from start of symptoms to Day 0 testing in the study. (Arm A)

Feasibility of SARS-CoV-2 antigen testing with a throat/nose or saliva lateral flow assay (Arm A)

Feasibility of SARS-CoV-2 antibody testing with a rapid lateral flow assay (Arms A & B)

Exploratory analyses:

Investigate antigen dynamics over time to compare with quantitative RT-PCR (Arm A)

To examine HLA-KIR interactions that shape CD8 anti-viral responses (Arms A&B)

To explore the relationship between host immune genotype (e.g. HLA-KIR) and peripheral blood immune phenotype with viral clearance (Arms A&B)

To investigate blood immune cell activation and transcriptome in participants (Arms A&B)

2. Objectives

This observational study will investigate how host cancer status and immune phenotype links to SARS-CoV-2 infection clinical presentation, seroconversion, and viral clearance. The study will also evaluate rapid antigen/antibody lateral flow tests.

3. Background

On 12 January 2020, a novel coronavirus was identified as the cause of an outbreak of unexplained pneumonia in Wuhan City, Hubei Province, China. This coronavirus was later named SARS-CoV-2, and the disease it causes COVID-19 [1].

SARS-CoV-2 is a non-segmented, positive sense RNA virus and part of the family of coronaviruses. Similar to the Systemic Acute Respiratory Syndrome (SARS) virus, it binds to the angiotensin-converting enzyme 2 (ACE2) receptor located on type II alveolar cells and intestinal epithelia. SARS-CoV-2 can result in a severe Acute Respiratory Distress Syndrome (ARDS) which is characterised by diffuse alveolar damage and direct viral cytopathic effect on pneumocytes [2]. Some patients who develop COVID-19 may respond with a fulminant “cytokine storm” reaction. Co-morbidities such as hypertension, kidney disease and diabetes have been linked to poorer prognosis and clinical outcomes. However, a proportion of patients of younger age and without comorbidities also develop severe disease.

As of 23 March 2020, a total of 374,921 COVID-19 cases have been reported in 168 countries with a total of over 16,411 deaths (case fatality amongst confirmed cases of 4.4%) [3] (John Hopkins's Coronavirus Resource centre). Over 293,425 cases and 13,258 deaths have been reported from countries outside mainland China. The World Health Organisation (WHO) declared on the 12th of March 2020 the SARS-CoV-2 outbreak a pandemic in the context of a Public Health Emergency of

International Concern (PHEIC). Europe has rapidly become the epicentre of the pandemic and in the UK, cases are increasing daily.

Based upon small observational studies, cancer patients are thought to be more susceptible in infection during a viral pandemic. In a retrospective analysis of 1524 patients with a diagnosis of COVID-19 at a tertiary care hospital in Wuhan, China, a history of cancer (n=18) were at a higher risk of SARS-CoV-2 infection (OR 2.31; 95% CI 1.89-3.02). [3] In a chart review of 355 fatal cases of SARS-CoV-2 infection in an Italian center, the median age of 79.5 years. The vast majority of patients had at least one medical co-morbidity. Strikingly, 20.8% patients had a history of cancer. [4] By contrast, an analysis of a UK-wide prospective database of cancer patients with COVID-19 infection (n=800) found the risk of death is driven mainly by age, gender and morbidities, rather than systemic anti-cancer therapy or radiotherapy. [5]

Amongst cancer patients at a French cancer centre, the rate of seroconversion 15 days after SARS-CoV-2 infection was 30% versus 71% when compared to healthcare workers. [6]

Little is known of the duration and severity of SARS-CoV-2 infection in cancer patients. Hence, SARS-CoV-2 pandemic poses of clinical dilemma in the provision of anti-cancer therapy. NICE guidance states the level of immunosuppression associated with treatments, capacity issues and the risk of cancer not being treated with the risk of immunosuppression and becoming seriously ill from SARS-CoV-2 infection. There is little data available which could inform clinicians on the timing of resumption of systemic anticancer treatment following recovery of SARS-CoV-2 infection. Similarly, the susceptibility of patients receiving immunotherapy to severe SARS-CoV-2 infection remains unclear.

Because of the lack of a validated serological test, the actual number, and therefore the proportion, of people that develop asymptomatic infections remains unknown. This means that an accurate case fatality estimate remains elusive. Due to the rise of the number of samples to diagnose, tests are taking longer than expected. Among the foremost priorities to facilitate public health interventions is a reliable laboratory diagnosis. Prompt case confirmation is necessary to ensure rapid and effective contact tracing, implementation of infection prevention and control measures according to WHO recommendations, and collection of relevant epidemiological and clinical information.

The SARS-CoV-2 antigen and antibody lateral flow assay (LFA) development has been led by Mologic, a company based in Bedford, England. We will use prototype LFA and ELISA that are ready for

preliminary evaluation, and subsequently use these tests on-site to evaluate the test at POC. LFA have been developed for SARS-CoV-2 antigen detection in throat/nose swabs and detection of IgG and IgM in blood/serum and SARS-CoV-2 antigen detection, IgG, IgM and IgA in saliva. Saliva is a convenient sample to use as it is far easier to use than blood or throat/nose swabs for potential self-testing.

The use of diagnostics developed within this study will improve the management of cases of COVID-19 in cancer patients. The LFA are rapid, easy to use and designed to be affordable globally. The rapid diagnosis of SARS-CoV-2 with antigen detection will allow cancer patients to be rapidly triaged in hospital and General practitioner (GP) surgeries. The use of antibody detection will allow both for diagnosis of immunological response to acute infections as well as after patients have recovered. To utilise these tests appropriately an understanding of dynamic immunopathological changes over time is necessary.

Characterisation of immune response and susceptibility and its association with viral clearance and disease progression in large cohorts with varied disease severity is important to assist clinical risk prediction outcomes and inform clinical decisions in relation to delaying cancer treatment. Immune response characteristics may have predictive and prognostic value, with early adaptive immune responses possibly correlated with improved clinical outcomes [7].

4. Rationale

This study is a collaboration between in the GI & Lymphoma Unit (RMH), the Infectious Diseases and Microbiology Units (St Georges Hospital) and our commercial partner Mologic Ltd who have been funded by DFID/Wellcome Trust to develop SARS-CoV-2 assays. This prospective study is intended to prospectively monitor cancer patients infected with SARS-CoV-2. This study will be valuable to understanding the clinical presentation and course of SARS-CoV-2 infection in this population as well as the virological parameters such as viral clearance by RT-PCR and IgM/IgG seroconversion. Serial measurement of SARS-CoV-2 antibody titres in asymptomatic individuals will provide insights into the longitudinal immune status of cancer patients.

This project will evaluate point-of-care/point-of-need (POC/PON) tests for the detection of the novel strain of coronavirus (2019 nCoV). We are working with Mologic Ltd, to develop a rapid, accurate and low cost, lateral flow assay (LFA) to detect viral circulating antigens and IgM/G against SARS-CoV-2 in less than 15 minutes. These POC/PON tests are intended for the rapid triage of patients

with fever and/or cough and to identify patients likely to be immune from previous infections. In addition, we will evaluate ELISA assays, also produced by Mologic to detect IgG and IgM (and possibly IgA) against SARS-CoV-2. Comparison of antibody and antigen dynamics over time will compare with ELISA and quantitative RT-PCR. Mologic have been instrumental in developing rapid tests for Ebola virus disease and dengue.

The ultimate diagnosis of SARS-CoV-2 is performed by laboratory testing as the clinical features are non-disease specific. Diagnostic testing of Covid-19 is currently undertaken using real-time reverse transcriptase PCR (RT-PCR) to detect the viral ribonucleic acid (RNA). These assays are sensitive but require transfer of samples to reference laboratories and thus results are obtained with a delay. In the UK, results are reported with a delay of 2-4 days, impeding the correct triage of patients, correct isolation measures and therefore putting the community and healthcare workers at risk.

A fast and reliable diagnostic assay that could be used at the POC is yet to be developed. Our collaborators have been working closely with Mologic Ltd in 2020 on the development of highly sensitive POC/PON tests to facilitate diagnosis at the point of need and to reduce the consequences of diagnostic delay. Dual antigen and antibody test development has been led by Mologic. We will use prototype lateral flow tests and ELISA that are ready for preliminary evaluation, and subsequently use the lateral flow tests at St Georges University of London to evaluate the test at the point of need. Left over and anonymised samples will be used to evaluate other diagnostics if appropriate, an amendment will be submitted if this is the case.

The information from our study will add significantly to the understanding of SARS-CoV-2 diagnostics and control and will improve the evidence-base for the management of cancer patients. Furthermore, data from this study could inform the timing and treatment for cancer patients who have recovered from SARS-CoV-2 infection.

This study may also serve as a valuable platform for assessing patients who may be at exceptional risk of a poor outcome with SARS-CoV-2 infection. Depending on the number of patients assessment for a biomarker of interest, exploratory analyses may be undertaken to assess the role of a prognostic or predictive role of these biomarkers in relation to the patients' clinical course and recovery.

SARS-CoV-2 can lead to acute respiratory distress syndrome (ARDS) and fulminant "cytokine storm". A recent case report of an immunocompetent patient diagnosed with a non-severe case of COVID-19

showed an increase in antibody-secreting cells (ASCs), immunoglobulin M (IgM), IgG antibodies follicular helper T cells (TFH cells), activated CD4+ T cells and CD8+ T cells. This patient did not experience ARDS or require supplemental oxygen and made a full recovery [7]. Evidence was provided of recruitment of immune cell populations (ASCs, TFH cells and activated CD4+ and CD8+ T cells), together with IgM and IgG SARS-CoV-2-binding antibodies, prior to resolution of symptoms.

These immunological changes appear to persist for at least 7 days following resolution of symptoms. The kinetics and immune responses associated with clinical resolution of COVID-19 were analysed, showing that ASCs and TFH were recruited as part of the immune response during the acute phase of COVID-19 illness and continued to be prominent during convalescence. ASCs appeared in the blood at the time of viral clearance (day 7; 1.48%) before peaking on day 8 (6.91%). TFH cells were shown to occur concurrently in blood at day 7 (1.98%) continuing to increase on day 8 (3.25%) and day 9 (4.46%) of illness. When compared to healthy control participants, the peak of both ASCs and cTFH cells was markedly higher in the patient with COVID-19 ($0.61\% \pm 0.40\%$ and $1.83\% \pm 0.77\%$, respectively (average \pm s.d.); $n = 5$) [7]. Given their immunosuppressed state, cancer patients are likely to have different immunological responses to COVID-19.

Secondary haemophagocytic lymphohistiocytosis (sHLH) is a hyperinflammatory syndrome characterised by a fulminant and fatal hypercytokinaemia leading to multiorgan failure, most frequently triggered by viral infections [8]. Cardinal features of sHLH include unremitting fever, cytopenias, and hyperferritinaemia. In a prospective cohort study of 41 patients confirmed to have COVID-19 disease a cytokine profile resembling sHLH was associated with disease severity. This profile was characterised by increased interleukin (IL)-2, IL-7, monocyte chemoattractant protein 1, macrophage inflammatory protein 1- α , and tumour necrosis factor- α , granulocyte-colony stimulating factor, interferon- γ inducible protein 10.

In a retrospective multicenter study comparing 68 death cases (68/150, 45%) and 82 discharged cases (82/150, 55%) in patients with laboratory-confirmed infection of SARS-CoV-2, a significant difference was seen in C-reactive protein (CRP) and interleukin-6 (IL-6) between the two groups [9].

Further work needs to be done urgently to characterise immune parameters in cohorts of cancer patients with COVID-19 with varied clinical presentations and disease severities to identify predictive and prognostic biomarkers. It is vital to investigate how cancer patients with an impaired immune

system links to viral clearance and seroconversion and this forms one of the underlying aims of our study. The impact of systemic anti-cancer therapy on the host immunity status is unclear.

5. Hypothesis

Arm A: We hypothesise that cancer patients with SARS-CoV-2 infection will acquire immunity by seroconversion (IgG/IgM) which is measurable by an ELISA assay. Furthermore, we hypothesise the study cohort will clear SARS-CoV-2 virus by analysis of throat/nose swab RT-PCR.

Arm B: We hypothesise systemic cancer treatments will result in a lower level of SARS-CoV-2 antibodies.

Arms A & B: We also hypothesise that antigen/antibody point of care testing by saliva, throat/nose swabs and blood will be a feasible diagnostic tool for the detection and monitoring of SARS-CoV-2 infection.

6. Aims

Arm A: This is a prospective study which aims to define the clinical characteristics of SARS-CoV-2 infection in cancer patients. The aim is to collect clinical data, throat/nose swabs, saliva and blood longitudinally to investigate viral clearance and seroconversion.

Arm B: The arm of the study will investigate the prevalence of SARS-CoV-2 antibodies amongst patients with cancer. Clinical data and blood samples will be collected longitudinally to assess the impact of systemic therapy on SARS-CoV-2 antibody titres.

In parallel, the study will also evaluate an antigen (Arm A) and IgG/IgM antibody (Arms A & B): point of care test (lateral flow assay) for the development of rapid detection of SARS-CoV-2.

7. End Points

7.1 Primary endpoint

Proportion of patients, at each sample timepoint, with a positive detection of IgM and IgG specific antibodies to SARS-CoV-2. Both IgM and IgG seroconversion will be reported separately. (Arms A & B)

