14.1 Sample size

Arm A

Based upon the current SARS-CoV-2 infection rates at the Royal Marsden NHS Foundation Trust, up to 60 patients (up to 50 patients with solid tumour or 10 with lymphoma) with confirmed SARS-CoV-2 infection by RT-PCR could be recruited in 6-9 months, assuming uptake of 40% (As per positivity rates in April 2020) in screening 150 patients.

For the primary endpoint, seroconversion, and the RT-PCR and LFA viral clearance secondary endpoints:

Arm A - Up to 60 SARS-CoV-2 positive patients are expected to be recruited in the study; the proportion of patients can be estimated with a 95% CI with a width of ±12.7%. In the 50 patient solid tumour cohort then this will be estimated with a 95% CI with a width of ±13.9%.

To account for lower recruitment rate of SARS-CoV-2 positive patients, the following table presents the maximum width of the 95% C.I.s, given a 50% observed proportion for the primary endpoint, according to different sample sizes (N).

An observed proportion of 50% has been selected, which is conservative and gives the widest possible 95% CI. (Table 4)

Table 4:

N	Proportion of patients, with a positive detection of IgM and IgG specific antibodies to SARS-CoV-2.	With of 95% CI
10	50%	± 31.0%
20	50%	± 21.9%
30	50%	± 17.9%
50	50%	± 13.9%
60	50%	± 12.7%

Arm B

For the primary endpoint up to 150 patients are expected to be recruited in Arm B. Considering a 10% antibody positivity rate [10], the proportion of patients can be estimated with a 95% CI with a width of ± 4.8%.

The clinical course of SARS-CoV-2 infection secondary endpoint is descriptive so no power calculation is required.

Due to the dynamic changes in the prevalence of SARS-CoV-2 infection during the pandemic, the study may be halted prematurely.

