14.2 Analysis plan

The primary endpoint will be presented as the proportion of patients at each sample time-point with 95% confidence interval Arms A and B will be reported separately.

Continuous data will be summarised as n, mean, standard deviation, median, minimum value and maximum value. Categorical data will be presented as frequencies and percentages.

Arm A:

The secondary endpoint, viral clearance, will be presented as the proportion of patients at each sample time-point with 95% confidence interval.

The clinical course of SARS-CoV-2 infection described as patient characteristics, and cancer diagnosis, will be summarised, as well as duration and severity of clinical symptoms, supportive treatments given, cancer treatments received and outcome of SARS-CoV-2 infection.

Feasibility of SARS-CoV-2 antigen testing with a lateral flow assay will be assessed by the following

- 1 Proportion of samples successfully processed and result obtained, with 95% confidence interval
- 2 Proportion of samples processed with a positive result by lateral flow, by the gold standard (throat/nose RT-PCR)

Arm B:

Feasibility of SARS-CoV-2 antibody testing with a lateral flow assay will be assessed by the following

- 1 Proportion of samples successfully processed and result obtained, with 95% confidence interval
- 2 Proportion of samples processed with a positive result by lateral flow, by the gold standard (SARS-CoV-2 laboratory serology test)

The formal statistical analysis plan will be developed based on the size of the available cohort and the performance of the experiment assays. The analysis will be developed in a separate molecular and statistical analysis plan which will be drafted and approved by the Trial Management Group (TMG) with statistical input. However, the above gives a guide as to the planned analyses.

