RT-PCR	Reverse Transcription-Polymerase Chain Reaction
SAP	Statistical Analysis Plan
SARS	Severe acute respiratory syndrome
SD	Standard deviation
SUSAR	Suspected unexpected serious adverse reaction
TMG	Trial management group

Amendment history

Date	Version	Timing in relation to analysis	Brief description of change	Justification for change
09.12.2021	1.0	First version prior to the final analysis	N/A	N/A

1. Study Summary

CARDS is an observational study which will investigate how host cancer status and immune phenotype links to SARS-CoV-2 infection clinical presentation, seroconversion, and viral clearance. The study will also evaluate rapid antigen/antibody lateral flow tests.

2. Study objectives

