5.2 Baseline patient characteristics

Patients will be described with respect to age, gender, cancer stage at diagnosis, anatomical site of malignancy, etc. Categorical data will be summarised by numbers and percentages. Continuous data will be summarised by mean, SD and range if data are normal and median, IQR and range if data are skewed. Minimum and maximum values will also be presented for continuous data.

6. Definitions of endpoints for analysis

Given that only one patient was recruited into Arm A, no analysis will be conducted on Arm A patients and all subsequent sections will refer to Arm B patients.

Pseudovirus neutralisation results are provided as continuous values, and currently there is limited research suggesting where the cut-off should lie in order to dichotomise the measurements into positive\negative neutralisation. Based on preliminary exploratory analysis run by the lab team at St. George's Hospital, we will dichotomise the pseudovirus neutralisation results using two different cut-offs: 0.5 and 0.8. Any endpoint involving pseudovirus neutralisation will be reported using each different cut-off.

Descriptive analysis on pseudovirus neutralisation results (summary statistics and boxplot by timepoint) will be included in the report.

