6.1 Primary endpoint

Proportion of patients at each sample timepoint (D0, D28, D56, D84) with a positive detection of IgG specific antibodies to SARS-CoV-2 (nucleocapsid and spike-protein). As part of a complete-case sensitivity analysis, proportions will be reported to include only patients who had a blood test at all timepoints.

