7.1 Primary endpoint

At each sample timepoint (D0, D28, D56, D84), the proportion of patients with a positive detection of (i) nucleocapsid antibodies and (ii) spike-protein antibodies will be reported alongside an exact two-sided 95% confidence interval. For the sensitivity analysis, the proportions will be reported in a similar manner except the denominators and numerators used to calculate each proportion will only include patients who had blood test results available at all timepoints (D0, D28, D56, D84).

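### Does the undefined word seroconversion leave a primary-endpoint analysis missing in Arm B?

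*Protocol*

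**What the plan says.** Protocol 7.1 sets the primary endpoint as the proportion with IgM and IgG detected at each sample timepoint, and continues: "Both IgM and IgG seroconversion will be reported separately. (Arms A & B"). Protocol 14.1 opens its Arm A precision statement with "For the primary endpoint, seroconversion, and the RT-PCR and LFA viral clearance secondary endpoints". Protocol 14.2 says: "The primary endpoint will be presented as the proportion of patients at each sample time-point with 95% confidence interval".

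For Arm B, Protocol section 6 says: "The arm of the study will investigate the prevalence of SARS-CoV-2 antibodies amongst patients with cancer". It adds the effect of systemic therapy on titres, and SAP 2.2 repeats both. Seroconversion appears in the Arm A aim (Protocol section 6, SAP 2.1) and in the whole-study summary in SAP section 1: "CARDS is an observational study which will investigate how host cancer status and immune phenotype links to SARS-CoV-2 infection clinical presentation, seroconversion".

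SAP section 6 then states: "Given that only one patient was recruited into Arm A, no analysis will be conducted on Arm A patients". For Arm B, SAP 6.1 defines the primary endpoint as "Proportion of patients at each sample timepoint (D0, D28, D56, D84) with a positive detection of IgG specific antibodies to SARS-CoV-2", and SAP 7.1 says that at each visit "the proportion of patients with a positive detection of (i) nucleocapsid antibodies and (ii) spike-protein antibodies will be reported" with an exact 95% interval. A repeat is restricted to patients with all four samples. SAP section 11 records that IgM is dropped and does not mention seroconversion.

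**The concern.** Seroconversion normally means a change from negative to positive. Estimating it needs a denominator of patients negative at the start. A per-visit proportion also counts patients already positive at D0, so it is seroprevalence. Between two visits, new positives and losses of antibody offset each other, and only the net change shows.

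Protocol 7.1 uses the word for both arms, inside the primary-endpoint section. With Arm A gone, Arm B is the only place the commitment could be met. If 7.1 promised a conversion proportion, the SAP has dropped part of the primary endpoint without listing it among its changes, and a reader might take the rise in per-visit positivity as the conversion rate.

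**Working it through.** **1. What the sample size was built for.** Inputs from Protocol 14.1: 150 Arm B patients, 10% positivity. Half-width = 1.96 × √(0.10 × 0.90 / 150) = 0.048, the stated ±4.8%. For Arm A, 1.96 × √(0.50 × 0.50 / 60) = 0.1265, the stated ±12.7%. Both use every patient in the arm as the denominator, and Table 4 heads its column as the proportion with antibody detected. The planned precision is that of a per-visit proportion, in the same paragraph that uses the word seroconversion.

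**2. What the per-visit tables cannot show.** In patients tested at both visits:

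new positives = (positive at D84 − positive at D0) + reversions

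Take the planning rate: 15/150 positive at D0, so 135 negative. Assume all 150 are retested. The documents give neither a D84 rate nor a reversion rate, so both are assumed here. Intervals are exact 95%.

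| Positive at D84 | Reversions among the 15 | New positives among 135 |
|---|---|---|
| 15/150 = 10.0% (5.7–16.0) | 0 | 0 = 0% (0–2.7) |
| 15/150 | 15 | 15 = 11.1% (6.4–17.7) |
| 18/150 = 12.0% (7.3–18.3) | 0 | 3 = 2.2% (0.5–6.4) |
| 18/150 | 3 | 6 = 4.4% (1.6–9.4) |
| 18/150 | 15 | 18 = 13.3% (8.1–20.3) |

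So 15/150 followed by 18/150 is compatible with 3 to 18 new positives. The narrower range of 3 to 6 holds only if reversion is capped at 20% (3 of 15). The complete-case repeat follows the same patients throughout, but it also shows only the net change.

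**3. Whether anything asks for conversion in Arm B.**

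- Protocol 14.1 places the word directly after the primary endpoint, as its name. Protocol 7.1 and 14.2 define and present that endpoint as positivity at each visit. Read together, the second sentence of 7.1 says that IgM and IgG are tabulated separately.
- SAP section 11 describes what the protocol had stated for IgM as positive detection, which is the same reading.
- The Arm B aim is prevalence and titres. The Arm B hypothesis (Protocol section 5) concerns antibody level under systemic treatment. Neither concerns incidence in D0-negative patients.
- SAP sections 6 and 7 never use the word. Their per-visit tables include D0, where a figure cannot be conversion since D0.

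**4. What a conversion table would add.** The blood and vaccine dates already exist, so it could be made. Its estimate is open to debate. Suppose 120, 100 and 80 still-negative patients are tested at D28, D56 and D84, with two new positives each time, and earlier converters stay in the denominator. The D84 figure is 6/(4 + 80) = 7.1% (2.7–14.9). Chaining the visits gives 1 − (118/120)(98/100)(78/80) = 6.0%. Missed visits push the first figure up.

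A single unconfirmed positive also counts as conversion. Three retests of 135 true negatives would give about 135 × 3 × (1 − specificity) false converters: 2, 4 or 8 at assumed specificities of 99.5%, 99% or 98%. In the second table scenario above, 3 to 6 new positives are at issue.

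**The case for a change.** The best argument for a change is that the word stands in the primary-endpoint section for both arms, that its usual meaning is negative to positive, and that nothing warns the reader otherwise. SAP 6.3.3 and section 11 also say the study has moved towards serological responses after infection or vaccination, which makes new positivity in D0-negative patients more interesting than it was. Section 11 lists other departures from the protocol but not this one.

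The factual part stands: the term is undefined, and no Arm B table has a D0-negative denominator. The inference does not. The protocol's own usage in 14.1 and 14.2 gives the word a workable meaning that the SAP follows. The shift of focus is served by the analyses split by vaccination status, by positivity counted from first vaccine, and by the fold rises. In the vaccinated group, the sensitivity analysis removes anyone nucleocapsid-positive up to that visit. That rule is cumulative, so later loss of antibody does not cancel it.

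One related observation is true but separate. Under SAP 4.3, a patient first vaccinated between D0 and the last sample is in neither the unvaccinated nor the vaccinated population, although some may fall in the second-dose population. Such patients stay in the overall spike proportion. That is a question about the population definitions, whatever seroconversion is taken to mean.

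**Conclusion.** No change is needed. Followed exactly, the plan gives sound per-visit seroprevalence with exact intervals, which is what the Arm B aim asks for. The gap is one of wording: a word used as a label for the primary endpoint and never defined. An analyst working from SAP sections 6 and 7 would fill it sensibly by reporting positivity as positivity. A note explaining the word would alter no number. A table of first positives among D0-negative patients would be a new endpoint that no Arm B aim requests, with an estimator that can lean high (7.1% against 6.0% in the illustration).

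This rests on reading Protocol 14.1 as naming the primary endpoint, which Table 4 and Protocol 14.2 support. If the authors did intend a conversion proportion in Arm B, that result is missing, and the per-visit tables could not replace it: unchanged prevalence of 10% fits conversion from 0% to 11.1%. Those figures assume the planning rate, full retesting of 150 patients and freely chosen reversion. They show what is not identifiable and do not predict this cohort.
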